**DAIDS-ES ID 12052**

**A non-IND study**

**HIV Vaccine Trials Network (HVTN) Clinical Research Site (CRS) filing instructions**

The following information impacts the HVTN 139 study and must be forwarded to your Institutional Review Board (IRB)/Ethics Committee (EC) and any other applicable Regulatory Entity (RE) as soon as possible for their information and review. Their approval is required before implementation.

Upon receiving final IRB/EC and any other RE approval(s) for this Letter of Amendment (LOA), CRSs must implement the LOA immediately.

Upon receiving final IRB/EC and any other applicable RE approval(s), CRSs are required to submit LOA registration documents to the DAIDS Protocol Registration Office (PRO) at the Regulatory Support Center (RSC). CRSs will receive an LOA Registration Notification once the DAIDS PRO verifies that all the required LOA registration documents have been received and are complete. A Registration Notification from the DAIDS PRO is not required prior to implementing the LOA. A copy of the LOA Registration Notification, along with this LOA and any IRB/EC and RE correspondence, should be retained in the CRS's regulatory files.

For additional information on the registration process and specific documents required for LOA registration, refer to the current version of the DAIDS Protocol Registration Manual.

The following information does not affect the sample informed consent. The CRS's IRB/EC is responsible for determining the process of informing study participants of the contents of this LOA.

## List of changes

Item 1	Revised in Section 5, Objectives and endpoints : secondary objective 4 moved to exploratory objective 5 .....	2
Item 2	Updated in Section 1.1, Protocol Team : Team membership, contact information, and roles.....	3

The changes described herein will be incorporated in the next version of Protocol HVTN 139 if it undergoes full protocol amendment at a later time. Added text is shown in **bold underline** and deleted text is shown with ~~strikethrough~~.

**Item 1    Revised in Section 5, *Objectives and endpoints*: secondary objective 4 moved to exploratory objective 5**

The secondary objective 4 has been moved to exploratory objective 5 since the assay data is not being used for clinical management of the participant. It will be used for research purposes only. Results may be used to identify pre-existing immunity that may interfere with other key immunology assessments.

**Tracked revised text in section 5.2: Secondary objectives and endpoints**

*~~Secondary objective 4:~~*

~~To evaluate vector specific antibodies both before and after vaccination.~~

*~~Secondary endpoint 4:~~*

~~Magnitude of serum antibody neutralization of AdC6 and AdC7 vectors as assessed by adenovirus neutralization assay at baseline (Parts A and B), 4 weeks after the first vaccination (Parts A and B), and 4 weeks after the second vaccination (Part B)~~

## Tracked revised text in section 5.3: Exploratory objectives

### Exploratory objective 5:

**To assess the magnitude of serum antibody neutralization of AdC6 and AdC7 vector both before and after vaccination.**

**Item 2 Updated in Section 1.1, *Protocol Team*: Team membership, contact information, and roles**

The Protocol Team list has been updated in Section 1.1, *Protocol Team*. Tracked revised text is shown below. Updated protocol team list is appended.

## Protocol modification history

Protocol modifications are made to HVTN protocols via clarification memos, letters of amendment, or full protocol amendments. HVTN protocols are modified and distributed according to the standard HVTN procedures as described in the HVTN Manual of Operations (MOP).

The version history of, and modifications to, Protocol HVTN 139 are described below.

### **Date: November 16, 2022**

---

*Protocol version: Version 1.0*

*Protocol modification: Letter of Amendment 2*

- Item 1 Revised in Section 5, *Objectives and endpoints*: secondary objective 4 moved to exploratory objective 5
- Item 2 Updated in Section 1.1, *Protocol Team*: Team membership, contact information, and roles

### **Date: May 19, 2022**

---

*Protocol version: Version 1.0*

*Protocol modification: Clarification Memo 2*

- Item 1 Updated in Appendix H, *Laboratory procedures Part B*; Appendix J, *Procedures at HVTN CRS for Part B*; and Appendix L, *HVTN 139 Visit Windows for Part B*: visit numbers for Part B

### **Date: March 07, 2022**

---

*Protocol version: Version 1.0*

*Protocol modification: Clarification Memo 1*

- Item 1 Updated in Section 8.3.1, *AdC6-HIVgp140*; Section 8.3.2, *AdC7-HIVgp140*; and 8.3.4, *Placebo for AdC6-HIVgp140 and AdC7-HIVgp140*: label of study products

### **Date: June 15, 2021**

---

*Protocol version: Version 1.0*

*Protocol modification: Letter of Amendment 1*

- Item 1 Revised in Section 4.10.1, *Clinical studies of Chimpanzee Ad vectors targeting diverse pathogens*, Section 4.11, *Potential risks of study products and administration*, Appendices A and B, *Sample Informed Consent Form for Part A and Part B (section 4)*, and Appendix N, *Adverse events of special interest: risks of AdC6 and AdC7 study products*
- Item 2 Revised in *Appendix A, Sample Informed Consent Form for Part A*, Sections 4 and 17: study product developer information

- Item 3 Revised in Appendix B, *Sample Informed Consent Form for Part B*, Section 4: study product developer information
- Item 4 Revised Section 1.1, *Protocol Team, Protocol Team Leadership*: Co-Chair and member contact information
- Item 5 Clarified in Section 9, *Clinic Procedures*: procedures for data entry into the study database and reference to the HVTN HIV testing algorithm
- Item 6 Clarified in Section 12, *Protocol conduct*: protocol monitoring
- Item 7 Updated Section 14, *Document references (other than literature citations)*: the URL for requirements for source documentation

**Date: February 23, 2021**

---

*Protocol version: Version 1.0*

*Protocol modification: N/A*

Original protocol

1 OVERVIEW

The following describes the Statistical Analysis Plan (SAP) for the analysis of immunogenicity data from HVTN 139 for Protocol Team (PT) reports for immunogenicity data, and the FSR for Immunogenicity.

2 PROTOCOL SUMMARY

Title

A phase 1 clinical trial to evaluate the safety and immunogenicity of HIV-1 vaccines based on chimpanzee serotypes of adenovirus expressing clade C gp140 and a CH505TF gp120 protein boost in healthy, HIV- uninfected adult participants.

Primary objective

To evaluate the safety and tolerability of AdC6-HIVgp140 and AdC7-HIVgp140 at doses of 1×10^{10} virus particles (vp) and 5×10^{10} vp, alone and in combination with CH505TF gp120 adjuvanted with GLA-SE in HIV- uninfected adults.

Study products and routes of administration

- **AdC6-HIVgp140:** a chimpanzee-derived replication-defective adenovirus (Ad) vector expressing codon optimized gp140 of clade C isolate Du422 administered at a dose of 1×10^{10} vp or 5×10^{10} vp. The vaccine dose will be divided equally into two separate 1mL intramuscular (IM) injections, administered into the deltoid of the non-dominant arm unless medically contraindicated.
- **AdC7-HIVgp140:** a chimpanzee-derived replication-defective Ad vector expressing codon optimized gp140 of clade C isolate Du172 administered at a dose of 1×10^{10} vp or 5×10^{10} vp. The vaccine dose will be divided equally into two separate 1mL IM injections administered into the deltoid of the non-dominant arm unless medically contraindicated.
- **CH505TF gp120:** CH505 transmitted/founder gp120 mixed with GLA-SE [the immunological adjuvant Glucopyranosyl Lipid A (GLA) in an oil-in-water stable emulsion (SE)], administered at a dose of 400 mcg with 10 mcg GLA-SE as a 1 mL injection in the thigh unless medically contraindicated.
- Placebo control for AdC6 -HIVgp140 and AdC7-HIVgp140 vaccine: Sodium Chloride for Injection, 0.9%, administered as two separate 1 mL IM injections into the deltoid of the non-dominant arm unless medically contraindicated.
- Placebo control for CH505TF gp120: Sodium Chloride for Injection, 0.9% administered as a 1 mL IM injection in the thigh unless medically contraindicated.

Participants

34 healthy, HIV– uninfected volunteers aged 18 through 50 years, inclusive; 30 vaccinees, 4 placebo recipients.

Schema

Table 2-1 Schema

Study arm	N	AdC dose (vp)	M0	M3	M6
Part A: Low Dose					
Group 1	5	1x 10 ¹⁰	AdC6-HIVgp140	-	-
Group 2	5	1x 10 ¹⁰	AdC7-HIVgp140	-	-
Group 3	2	0	Placebo	-	-
Part B: High Dose					
Group 4	10	5 x 10 ¹⁰	AdC6-HIVgp140	AdC7-HIVgp140	400 mcg CH505TF gp120/GLA-SE
Group 5	10	5 x 10 ¹⁰	AdC7-HIVgp140	AdC6-HIVgp140	400 mcg CH505TF gp120/GLA-SE
Group 6	2	0	Placebo	Placebo	Placebo
Total	34 (30 vaccinees / 4 placebos)				

Notes:

Study is blinded as to Group assignment (Part assignment is not blinded). Enrollment will be stepwise starting with Part A. To ensure the safety of participants, a series of pre-planned enrollment pauses will occur.

Safety Review #1: Low-dose Initial Vaccination. Enrollment for Part A will be restricted to a maximum of 1 participant per day across all participating HVTN Clinical Research Sites (CRSs) until a total of 5 participants have been enrolled. The HVTN Protocol Safety Review Team (PSRT) will review available safety and reactogenicity data reported for each of these 5 participants, up to and including the data reported for the first 72 hours postvaccination for the 5th enrolled participant, and determine whether it is safe to proceed with full enrollment in Part A.

Safety Review #2: Low-dose (Part A) Safe-to-Proceed. The HVTN PSRT will review cumulative safety data, including at a minimum the 2-weeks following the vaccination visit, available on all 12 participants in Part A to determine whether dose-escalation may occur from Part A to Part B.

Safety Review #3: Full Enrollment at Targeted Dose. The HVTN PSRT will also review cumulative safety data available on the first 12 participants enrolled in Part B, including the 2-week post Month 0 vaccination visit, to determine whether it is safe to proceed with full enrollment.

Design

Multicenter, randomized, controlled, double-blind trial.

Safety monitoring

HVTN139 PSRT; HVTN Safety Monitoring Board (SMB)

3 OBJECTIVES AND ENDPOINTS

3.1 Primary

Primary objective 1:

To evaluate the safety and tolerability of AdC6-HIVgp140 and AdC7-HIVgp140 at doses of 1×10^{10} virus particles (vp) and 5×10^{10} vp, alone and in combination with CH505TF gp120 adjuvanted with GLA-SE in HIV- uninfected adults.

Primary endpoint 1:

Local and systemic reactogenicity signs and symptoms for a minimum of seven days following receipt of any study product. All adverse events for thirty days after any receipt of study vaccination. All serious adverse events (SAEs) medically attended adverse events (MAAEs), and adverse events of special interest (AESIs) will be collected for twelve months following any receipt of study product.

3.2 Secondary

Secondary objective 1:

To evaluate and compare immune responses elicited by single administration of AdC6-HIVgp140 or AdC7-HIVgp140 at two different dose levels.

Secondary endpoints 1:

- Response rate, magnitude, and breadth of HIV-specific serum IgG binding antibodies assessed 4 weeks after a single vaccination (Part A) or the first vaccination (Part B)
- Response rate, magnitude, and polyfunctionality of HIV-specific CD4+ and CD8+ T-cell responses assessed 4 weeks after a single vaccination (Part A) or the first vaccination (Part B)
- Response rate, magnitude, and breadth of serum neutralizing antibodies against tier 1 and if applicable, other heterologous tier 2 HIV-1 isolates assessed 4 weeks after a single vaccination (Part A) or the first vaccination (Part B)

Secondary objective 2:

- To evaluate and compare immune responses elicited by sequential administration of AdC7-HIVgp140 followed by AdC6-HIVgp140 and AdC7-HIVgp140 followed by a dose of AdC6-HIVgp140 at 5×10^{10} vp

Secondary endpoints 2:

- Response rate, magnitude, and breadth of HIV-specific serum IgG binding antibodies assessed 4 weeks after the second vaccination (Part B)
- Response rate, magnitude, and polyfunctionality of HIV-specific CD4+ and CD8+ T-cell responses assessed 4 weeks after the second vaccination (Part B)

- Response rate, magnitude, and breadth of serum neutralizing antibodies against tier 1 and if applicable, other heterologous tier 2 HIV-1 isolates assessed 4 weeks after the second vaccination (Part B)

Secondary objective 3:

To evaluate and compare immune responses elicited by heterologous AdC7-HIVgp140 followed by AdC6-HIVgp140 or AdC7-HIVgp140 followed by AdC6-HIVgp140 prime followed with CH505TF gp120 / GLA-SE boost.

Secondary endpoints 3:

- Response rate, magnitude, and breadth of HIV-specific serum IgG binding antibodies assessed 2 weeks after the third vaccination (Part B)
- Response rate, magnitude, and polyfunctionality of HIV-specific CD4+ and CD8+ T-cell responses assessed 2 weeks after the third vaccination (Part B)
- Response rate, magnitude, and breadth of serum neutralizing antibodies against tier 1 and if applicable, other heterologous tier 2 HIV-1 isolates assessed 2 weeks after the third vaccination (Part B)

3.3 Exploratory

Exploratory objective 1:

To characterize antibody avidity and/or Fc-mediated antibody functions (infected cells antibody binding assay [ICABA], antibody-dependent cellular cytotoxicity [ADCC], antibody dependent cellular phagocytosis [ADCP], antibody dependent neutrophil phagocytosis [ADNP], and FcR-binding)

Exploratory objective 2:

To assess the impacts of vaccination on B-cell subset distribution in blood

Exploratory objective 3:

To conduct analyses related to furthering the understanding of HIV, immunology, vaccines, and clinical trial conduct.

Exploratory objective 4:

To further evaluate immunogenicity of each vaccine regimen, additional immunogenicity assays may be performed, including on samples from other timepoints, based on the HVTN Laboratory Center assay portfolio.

Exploratory objective 5:

To assess the magnitude of serum antibody neutralization of AdC6 and AdC7 vector both before and after vaccination.

4 COHORT DEFINITION

All data from enrolled participants will be analyzed according to the initial randomization assignment regardless of how many vaccinations they received. In the rare instance that a

participant receives the wrong treatment at a specific vaccination time, the Statistical Analysis Plan (SAP) will address how to analyze the participant's safety and immunogenicity data. Analyses are modified intent-to-treat in those individuals who are randomized but not enrolled do not contribute data and hence are excluded. Because of blinding and the brief length of time between randomization and enrollment—typically no more than 4 working days—very few such individuals are expected.

5 POTENTIAL CONFOUNDERS

Characterization of the safety of the vaccine is susceptible to confounding by adverse events not related to the vaccine that by chance occur more often in one arm of the trial than another. Therefore, analyses involving adverse events will incorporate the reported relationship to product as assessed by HVTN staff.

6 RANDOMIZATION

A participant's randomization assignment will be computer generated and provided to the HVTN CRS pharmacist through a Web-based randomization system. At each institution, the pharmacist with primary responsibility for dispensing study products is charged with maintaining security of the treatment assignments (except in emergency situations as specified in the HVTN MOP).

7 BLINDING

Participants and site staff (except for site pharmacists and other staff designated for pharmacy quality control) will be blinded as to participant treatment group assignments (eg, vaccine or control) but not to study part. Safety assessments will be made in a blinded fashion until the planned unblinding occurs (see protocol **Error! Reference source not found.**, **Error! Reference source not found.**, **Error! Reference source not found.**, and **Error! Reference source not found.**).

Study product assignments are accessible to those HVTN CRS pharmacists, DAIDS protocol pharmacists and contract monitors, and SDMC staff who are required to know this information in order to ensure proper trial conduct. Any discussion of study product assignment between pharmacy staff and any other HVTN CRS staff is prohibited excepted for designated staff used solely for the purposes of quality control. The HVTN SMB members also are unblinded to treatment assignment in order to conduct review of trial safety.

When a participant leaves the trial prior to study completion, the participant will be told he or she must wait until all participants are unblinded to learn his or her treatment assignment.

In some cases, the CRS, PSRT, or study sponsor may believe unblinding of the site PI and participant would be appropriate to facilitate the clinical management of an AE or SAE. The HVTN Unblinding MOP specifies procedures for emergency unblinding, and for early unblinding for medical reasons.

8 STATISTICAL ANALYSIS

This section describes the final study analysis, unblinded as to treatment arm assignment. All data from enrolled participants will be analyzed regardless of how many vaccinations they received. All analyses will be performed using SAS and/or R.

8.1 Immunogenicity analysis

8.1.1 General approach

For the statistical analysis of immunogenicity endpoints, data from enrolled participants will be used according to the initial randomization assignment regardless of how many injections they received. Additional analyses may be performed, limited to participants who received all scheduled injections per protocol. Assay results that are unreliable are excluded; results from specimens collected outside of the visit window, from HIV-infected participants post-infection or from participants with study product administration errors due to wrong dose administered, may be excluded. Since the exact date of HIV infection is unknown, any assay data from blood draws 4 weeks prior to an infected participant's last seronegative sample and thereafter may be excluded. If an HIV-infected participant does not have a seronegative sample post-enrollment, then all data from that participant may be excluded from the analysis.

Discrete categorical assay endpoints (eg, response rates) will be analyzed by tabulating the frequency of positive response for each assay by antigen and treatment arm at each timepoint for which an assessment is performed. Crude response rates and difference between treatment arms will be presented with their corresponding 95% confidence interval estimates calculated using the score test method [1].

For quantitative assay data, graphical and tabular summaries of the distributions by antigen, treatment arm, and timepoint will be made. For all primary and secondary immunogenicity endpoints, box plots and plots of estimated reverse cumulative distribution curves will be used for graphical display of all study arms. Typically, the results will be shown for each vaccine arm and for the set of control arms pooled into one group.

Mean or median (if normality assumption severely violated) assay readouts will be compared between arms and bootstrap confidence intervals will be estimated.

More sophisticated analyses employing repeated measures methodology (for example, linear mixed models or marginal mean models fit by generalized estimating equations) may be utilized to incorporate immune responses over several timepoints and to test for differences over time. However, inference from such analyses would be limited by the small sample size of this study. All statistical tests will be 2-sided and will be considered statistically significant if $p \leq 0.05$.

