9.2.1 Lists of Tables

- Response rate table by lab, T-cell subset, cytokine, peptide pool, visit, visit month, and treatment arm for cells expressing a given cytokine using Fisher's exact test criteria.
- Summary statistics of background-adjusted marginal cytokine response magnitude (i.e., min, mean, median, max) among all participants (positive and negative responders) for T-cell subset, cytokine, peptide pool, visit, and treatment arm.
- Summary statistics of background-adjusted marginal cytokine response magnitude (i.e., min, mean, median, max) among responders for T-cell subset, cytokine, peptide pool, visit, and treatment arm.
- Response rate and/or response magnitude comparison of treatment arms.
 - a. Treatment 1 vs. Treatment 4 at 4 weeks after 1st vaccination
 - b. Treatment 2 vs. Treatment 5 at 4 weeks after 1st vaccination
 - c. Treatment 4 vs. Treatment 5 at 4 weeks after 1st vaccination, 4 weeks after 2nd vaccination, 2 weeks after 3rd vaccination, and 6 months after 3rd vaccination

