9.4.1 List of Tables

- Response rate table by lab, isotype, antigen, visit number (visit month), and treatment arm
- Summary statistics of net MFI values (i.e., min, mean, median, max) among all participants (positive and negative responders) by lab, isotype, antigen, visit number (visit month), and treatment arm, upon request.
- Summary statistics of net MFI values (i.e., min, mean, median, max) among responders by lab, isotype, antigen, visit number (visit month), and treatment arm.
- Summary statistics of binding antibody titers (AUC) (i.e., min, mean, median, max) among all participants (positive and negative responders) by lab, isotype, antigen, visit number (visit month), and treatment arm, upon request.
- Summary statistics of binding antibody titers (AUC) (i.e., min, mean, median, max) among responders by lab, isotype, antigen, visit number (visit month), and treatment arm.
- Comparison of response rates between different doses (T1 vs T4, T2 vs T5) at 4 weeks post one vaccination, by product, isotype, and antigen
- Comparison of net MFI values between different doses (T1 vs T4, T2 vs T5) at 4 weeks post one vaccination, by isotype, and antigen among all participants and among positive responders.
- Comparison of binding antibody titers (AUC) between different doses (T1 vs T4, T2 vs T5) at 4 weeks post one vaccination, by isotype, antigen, and visit among all participants and among positive responders.
- Comparison of response rates between different sequential administration in Part B (T4 vs T5) at 4 weeks post the 2nd vaccination and 2 weeks post the 3rd vaccination, by product, isotype, and antigen
- Comparison of net MFI values between different sequential administration in Part B (T4 vs T5) at 4 weeks post the 2nd vaccination and 2 weeks post the 3rd vaccination, by isotype, antigen, and visit among all participants and among positive responders.
- Comparison of binding antibody titers (AUC) between different sequential administration in Part B (T4 vs T5) at 4 weeks post the 2nd vaccination and 2 weeks post the 3rd vaccination, by isotype, antigen, and visit among all participants and among positive responders.
- Differential binding response rates by isotype, differential binding antigen pair, visit, and treatment arm.
- Summary statistics of differential binding response ratio (i.e., min, mean, median, max) by lab, isotype, antigen pair, visit number (visit month), and treatment arm.

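### Minor: read literally, the optional all-injections subset conditions Month 1 and Month 4 results on later vaccinations and sets unequal entry rules for the Month 1 dose comparison

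*SAP*

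**What the plan says.** SAP section 8.1.1 makes the as-randomised set the main one for immunogenicity: "data from enrolled participants will be used according to the initial randomization assignment regardless of how many injections they received". Sections 4 and 8 say the same. Section 8.1.1 then permits a supportive set: "Additional analyses may be performed, limited to participants who received all scheduled injections per protocol". No other section of the SAP narrows that set to injections due before a given visit, or defines it by timepoint or assay.

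The schedule is in Table 2-1 (section 2). The Part A row reads "Group 1 5 1x 10 ¹⁰ AdC6-HIVgp140", with nothing at Month 3 or Month 6. The corresponding Part B row reads "Group 4 10 5 x 10 ¹⁰ AdC6-HIVgp140 AdC7-HIVgp140 400 mcg CH505TF gp120/GLA-SE", one product at each of Months 0, 3 and 6. Groups 2 and 5 follow the same pattern with the vectors exchanged, and the placebo groups follow the schedule of their own Part.

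Secondary objective 1 compares two dose levels, and section 3.2 times its endpoints as "assessed 4 weeks after a single vaccination (Part A) or the first vaccination (Part B"). The matching comparisons cross the Parts. Section 9.2.1 (ICS) lists "Treatment 1 vs. Treatment 4 at 4 weeks after 1st vaccination" and the same for Treatments 2 and 5. Section 9.3.1 (neutralisation) lists both pairs. Section 9.4.1 (binding antibody) has "Comparison of response rates between different doses (T1 vs T4, T2 vs T5) at 4 weeks post one vaccination".

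**The concern.** Whether a participant belongs to the supportive set is settled only once the last scheduled vaccination has been given or missed. In Part B that is Month 6, after both the Month 1 and the Month 4 samples.

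Take a Group 4 participant who receives the first vaccination, gives a valid Month 1 sample and then stops. Vaccinations two and three could not have influenced that sample, yet the set drops it. A Group 1 participant with the same experience after the first vaccination stays, because nothing further was scheduled. The two sides of T1 v T4 are therefore selected by different rules. At Month 4 (secondary objective 2), a participant who had the first two vaccinations but missed the third is dropped in the same way.

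Two things are at stake in that supportive analysis. Valid data are lost from arms of 10. There is also possible selection bias, because stopping may follow reactogenicity and reactogenicity may be related to immune response. Section 8 describes the final analysis as unblinded, so a loosely defined optional set leaves its meaning to be settled after the results can be seen.

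**Working it through.** The plan gives no subset size, missed-dose rate or effect size, so there is no figure of its own to reproduce. The first two steps are counts from the documents. The rest is illustration under stated assumptions.

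**1. Arms (SAP Table 2-1).** 5 + 5 + 2 + 10 + 10 + 2 = 34. Vaccinees: 5 + 5 + 10 + 10 = 30. This agrees with "30 vaccinees, 4 placebo recipients".

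**2. What membership requires.** Section 2 gives each AdC vaccination, or its placebo, as two injections and the protein boost as one.

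| | Part A | Part B |
|---|---|---|
| Vaccinations required | 1 | 3 |
| Injections required | 2 | 2 + 2 + 1 = 5 |
| Still to come at Month 1 | 0 | 2 vaccinations |
| Still to come at Month 4 | not applicable | 1 vaccination |
| Still to come at Month 6.5 | not applicable | 0 |

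**3. How many might be lost.** Assume everyone enrolled receives the first vaccination, and each later one is missed independently with probability q. Expected Part B retention is (1 − q)², against 100% in Part A. The chance that an arm of 10 loses at least one member is 1 − (1 − q)^20.

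| q (assumed) | Part B retained | Chance that ≥ 1 of 10 is lost |
|---|---|---|
| 5% | 90% | 64% |
| 10% | 81% | 88% |
| 15% | 72% | 96% |
| 20% | 64% | 99% |

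**4. Possible shift in a mean.** Assume a normal readout with SD 1, and that the most reactogenic one or two of 10 stop after the first vaccination. The two largest expected order statistics of 10 standard normals are 1.539 and 1.001. If reactogenicity tracked response perfectly:
- one stops: −1.539/9 = −0.171 SD
- two stop: −(1.539 + 1.001)/8 = −0.318 SD

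Multiplying by an assumed correlation of 0.3 to 0.8:
- one stops: 0.3 × 0.171 = 0.05 to 0.8 × 0.171 = 0.14 SD
- two stop: 0.3 × 0.318 = 0.10 to 0.8 × 0.318 = 0.25 SD

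The Part A arm does not move. With no correlation the shift is zero.

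**5. Possible shift in a response rate.** Assume a true Month 1 rate of 60% at both doses. The subset rate is p·r1/(p·r1 + (1 − p)·r0), where r1 and r0 are the retention of responders and non-responders.
- r1 = 0.7, r0 = 0.9: 0.42/(0.42 + 0.36) = 53.8%, about 6 points low
- r1 = 0.9, r0 = 0.7: 0.54/(0.54 + 0.28) = 65.9%, about 6 points high
- r1 = r0: 60%, no bias

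**6. Precision.** SE of a difference in means = √(1/n1 + 1/n2), in SD units, with two lost per Part B arm:
- T4 v T5: √(1/10 + 1/10) = 0.447 rises to √(1/8 + 1/8) = 0.500 (+12%)
- T1 v T4: √(1/5 + 1/10) = 0.548 rises to √(1/5 + 1/8) = 0.570 (+4%)

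**7. With a visit-based set.** Month 1 requires the first vaccination in every arm, so under the assumption in step 3 retention in T4 and T5 returns from (1 − q)² to 100%. At Month 4 it rises from (1 − q)² to (1 − q). At Month 6.5 it is unchanged.

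**The case against.** The strongest reply is that this set is optional and supportive. The listed T1 v T4 and T2 v T5 comparisons are not tied to it, and the as-randomised analysis keeps every sample in question. That stands, and it is why the point is minor. A reader might infer that the planned dose contrasts are themselves biased. They are not: at Month 1 the main set retains a Part B participant who stops after the first vaccination.

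A reader might also infer that neither set serves objectives 2 and 3. For objective 3 this is wrong. At Month 6.5 no scheduled vaccination remains, so the set is exactly those who had all three. Nor is the as-randomised set at fault for counting people who missed doses. It follows the modified intent-to-treat principle of section 4 and answers a different, legitimate question.

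Further limits also stand:
- The unequal requirement affects only cross-Part comparisons. T4 and T5 both need three vaccinations, so there only the conditioning on later doses applies. Placebo Group 6 also needs three, so the stricter rule is a Part B feature, not a high-dose one.
- Parts A and B enrol stepwise (section 2), so T1 v T4 is not a concurrent randomised contrast in any set.
- The largest shift in the illustrated range, 0.25 SD, is less than half the 0.570 SD standard error of T1 v T4.
- A fixed completer cohort keeps one denominator across visits, which helps the over-time analyses that section 8.1.1 contemplates.
- The sponsor may intend injections due up to the visit. The protocol text available is a letter of amendment and modification history, so a fuller definition elsewhere cannot be ruled out.

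The reply does not supply the missing qualifier. As the SAP is worded, whoever runs this analysis would drop valid Month 1 and Month 4 samples.

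**Conclusion.** The point holds as a minor defect in the definition of an optional set. Taken literally, section 8.1.1 selects Part B participants on vaccinations due after the Month 1 and Month 4 samples, and applies unequal entry rules to T1 v T4 and T2 v T5 at Month 1. The mismatch itself follows directly from Table 2-1 and needs no assumption.

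Any bias needs completion of later doses to be related to response; otherwise only precision is lost. Its size cannot be determined from the documents. The range of about 0.05 to 0.25 SD rests on a normal readout, one or two of the most reactogenic of 10 stopping after the first vaccination, and a correlation of 0.3 to 0.8, all of them assumed. The direction is also unknown, as the response-rate illustration shows. The main analysis is unaffected at every visit, and the supportive set needs no change at Month 6.5 or later.

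**What to change.** Replace the sentence in SAP section 8.1.1 with wording such as: *Additional analyses at a given visit may be limited to participants who received all injections scheduled before that visit, regardless of later injections.* Month 1 then requires the first vaccination only, in both Parts. Month 4 requires the first two. Month 6.5 and Month 12 require all three, as now.

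The cost is one sentence and a visit-level flag in the analysis dataset, with no new data. The downside is that the per-protocol denominator differs by visit, so each table should show it. If a single completer cohort is wanted for over-time displays, it can be kept for that purpose under its own name.
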